1.0 Synopsis

Title	A prospective, observational study to examine the effects of ageing on the clinical outcomes of people living with HIV in England and Ireland.
Study name	POPPY – ‘ P harmacokinetic and C linal O bservations in P eople over F ifty’
Study aims:	
 1. To analyse the incidence and outcomes of co-morbidities in older-HIV-positive people and their relationship with demographic/clinical factors. 2. To evaluate associations between antiretroviral drug concentrations and age, and to assess the potential impact of age on drug efficacy, drug-drug interactions and co-morbidities. 3. To contribute to the development and implementation of evidence-based recommendations for the clinical monitoring of older HIV-positive patients.
Target Population (summary)	
Older HIV-positive cohort (n=1000):
 
 • documented HIV infection • age ≥ 50 years at study entry • self defined white or black African ethnicity • likely route of HIV acquisition via sexual exposure Either by male to male exposure if white or by heterosexual exposure if white or black African • able to comprehend study patient information leaflet 
Younger HIV-positive cohort (n=500):
 
 • documented HIV infection • age <50 at study entry • self defined white or black African ethnicity • likely route of HIV acquisition via sexual exposure Either by male to male exposure if white or by heterosexual exposure if white or black African • able to comprehend study patient information leaflet 
HIV-negative cohort (n=500):
 
 • documented negative HIV test in past 6 months or documented at screening • age ≥ 50 years at study entry • self defined white or black African ethnicity
Design	Multicentre, prospective, observational study over 3 years
Study visits	
The study will comprise of four study visits:
 
 1. Screening 2. Visit 1 (Baseline visit) 3. Visit 2 (1st year follow up visit) – HIV infected cohorts only

	
Phone visit 2 (1st year follow up visit) – HIV negative cohorts only
 
4. Visit 3 (2nd year follow up visit)
 
The study visits are expected to take 1-2 hours to complete and will include the following assessments (see main protocol for full description)
 
 • Baseline demographics. • Socio-economic status. • Anthropometrics. • Lifestyle factors. • Quality of life assessment. • Full clinical history: to include history of non-AIDS co-morbidities • Menstrual and reproductive history (women) • Family medical history. • Current and recent antiretroviral use (over past 12 months). • Duration of HIV infection and date of HIV-seroconversion if known • Adherence assessment. • Use of any other medications. • Neurocognitive function assessment. • Pain assessment. • DXA scan A full body where available for bone mineral density, otherwise simple a scan of spine and hips will be performed. • Falls risk, Fracture risk, Frailty assessment • Most recent routine laboratory tests will be recorded and will be assessed in the HIV-negative cohort • Blood (serum, plasma, and PBMC) and urine samples stored Blood (plasma) will be collected for pharmacokinetic analysis (including but not limited to antiretroviral drug exposure)
Sample Size	Our choice of sample size is largely pragmatic, reflecting the number of older patients receiving care and the proportion that are expected to participate. Detailed sample size calculations are difficult given the wide range of topics and methodological approaches proposed. However, power calculations for some exemplar projects are provided.

1.1	Table of contents.	
1.0	Synopsis.....	3
1.1	Table of contents.....	5
2.0	Schedule of Visits	6
3.0	Introduction	7
3.1	Background – The HIV epidemic in the UK and Ireland	7
3.2	Clinical manifestations of ageing in HIV.....	7
3.3	Justification for the study.....	9
3.4	Study team	9
3.5	Summary	9
3.6	References.....	9
4.0	Study Plan	11
4.1	Study population	11
4.2	Setting	12
4.2.1	Recruitment of HIV-positive cohorts.....	12
4.2.2	Recruitment of HIV-negative cohort	13
4.3	Study Objectives.....	13
5.0	Study visits	13
5.1	Screening.....	13
5.2	Visit 1 (Baseline visit).....	13
5.3	Visit 2 (1st year follow up visit)	14
5.4	Visit 3 (2nd year follow up visit)	15
5.5	Withdrawal of subjects from study.....	15
5.6	Study timelines.....	16
5.7	Sub-Study	16
5.8	End of trial definition	16
6.0	Study Specific Procedures.....	16
6.1	DEXA scanning.....	16
6.2	Blood sampling	16

2.0 Schedule of Visits

Study Visit	Screening	Baseline	Follow up visits	
	Within 60 days of baseline	Visit 1	Visit 2 (12 months after visit 1) HIV positive cohorts only	Visit 3 (24 months after visit 1)
Informed Consent	x			
Review Eligibility	x	x		
Detailed medical history as per protocol		x	x	x
Study Questionnaire		x	x	x
Respiratory questionnaire				x
Neurocognitive assessment		x		x
DXA scan			x	
Blood sampling		x		x
Phone contact			x (HIV negative cohort)	x

3.0 Introduction

3.1 Background – The HIV epidemic in the UK and Ireland

Despite the availability of combination antiretroviral therapy (cART), HIV continues to place a major burden on the NHS. During 2009, 60,240 HIV-positive individuals received care for HIV in England, with 6,630 new diagnoses that year¹. The lifetime costs of HIV infection (with a projected life expectancy of 26.4 years) have been estimated at £17,000 per year².

The pattern of the HIV epidemic has undergone dramatic change over the last decade, most notably in terms of the ageing of the HIV-positive population. Of those receiving care for HIV in England in 2009, 18.4% were aged ≥ 50 years, an increase from 11.0% in 2000¹. This is largely due to the use of cART which has led to increased life expectancy³. However, older individuals continue to be newly diagnosed with HIV (12.9% of those newly diagnosed in 2009 were aged ≥ 50 years). Projections from the UK CHIC Study suggest that by 2015, 27% of those seen for care will be aged ≥ 50 years. Whilst an age of 50 would not normally be considered as old, this cut-off reflects the fact that prior to cART few people were expected to survive to this age.

Across the UK, those of white or black African ethnicity, and those acquiring HIV via sexual routes accounted for 84% of older people receiving care for HIV in 2009 [[name], personal communication]. The clinics that will participate in the POPPY study have provided care for $>27,000$ HIV-positive individual since 1996. Of the patients seen for care at these clinics in 2008/9, 12,620 fell into one of these target groups of whom around 19% were aged >50 years at their most recent visit (Table 1).

Table 1: Characteristics of patients seen at participating clinics in 2008/09

		Age at most recent visit in 2008/09	
		16-49 years	>50 years
Number of patients		10202	2418
Age (years)	Median	39	55
Gender	Male	78%	90%
	Female	22%	10%
Sexual orientation	Homosexual	66%	77%
	Heterosexual	32%	22%
Ethnicity	White	73%	87%
	Black African	26%	13%
Receiving cART		74%	90%
CD4 count (cells/mm ³)	Median	480	450
Prior AIDS diagnosis		16%	30%

3.2 Clinical manifestations of ageing in HIV

Bone manifestations

Older HIV-positive people experience significantly more medical co-morbidities than younger individuals^{4,5}. In particular, low bone mineral density (BMD) and osteoporosis are prevalent, with HIV-positive patients being over six times as likely to have decreased BMD and four times as likely to have osteoporosis than HIV-negative counterparts⁶. The main clinical consequence of osteoporosis is fractures, which arise from poor bone health (osteoporosis) and increased falls (due to increased fragility or instability). In the general population, fracture rates increase dramatically in those aged >70 years; in HIV-positive people, fractures are more frequent and occur at a younger age⁷. High rates of vitamin D deficiency, of particular importance for bone health, have been observed in HIV-positive patients⁸ and the initiation of cART is associated with further BMD loss and increased bone turnover⁹. As the HIV-positive population ages, it is important to determine the contributions of low BMD,

hypovitaminosis D, cART exposure and fragility to fracture incidence, to identify the age at which fracture risk starts to increase, and the extent to which existing risk prediction tools (e.g. FRAX¹⁰) accurately predict fracture risk in these patients.

Cerebral function

High rates of neurocognitive (NC) function impairment have been reported in HIV positive subjects on successful cART^{11,12}. Prior to cART, HIV-associated brain disease often presented as a frank dementia process (HIV-associated dementia, HAD) with a high associated mortality¹³. In recent years, a milder form of this process (HIV-related NCI) is more often observed; this is associated with progression to HAD¹⁴, poor adherence to cART, and difficulties in obtaining employment. An understanding of the factors associated with the development and progression of NC impairment is essential for the successful, long-term management of this population. Older age, viral hepatitis C co-infection and treatment with antiretroviral drugs lacking penetration into the CNS have been implicated as risk factors for HIV-related NC impairment. Although cognitive decline is part of the normal ageing process, differences in the patterns of cognitive decline have been reported between age-related and HIV-related cognitive decline¹⁵.

Renal function

Chronic kidney disease has been reported in 17% of HIV positive patients, and increasing age is an independent risk factor¹⁶. Glomerular filtration rate declines with age, and people over 60 years have 20–30% lower GFR than those under 50 years¹⁷. Age-related decline in renal function is associated with co-morbidities including hypertension, diabetes mellitus, and atherosclerotic, cardiovascular and urological disease¹⁸. Serum phosphate levels decline with age as a result of impaired tubular phosphate reabsorption¹⁹ and declining muscle mass results in lower serum creatinine concentrations. Elderly patients often use multiple medications, many of which are excreted via the kidney. Altered body composition and impaired renal function contribute to altered pharmacokinetics and pharmacodynamics in older patients, and may lead to an increased incidence of nephrotoxicity and systemic side effects. In addition, renal failure and altered renal tubular function may affect bone mineralisation.

Musculoskeletal

Research into musculoskeletal manifestations and pain has been neglected in HIV-positive adults. A recent survey in Brighton of >850 respondents found a prevalence of current pain of 63%, with 80% of those with pain having had symptoms for >3 months and one in 4 of these patients meeting the criteria for chronic widespread pain²⁰. In HIV-negative adults, chronic widespread pain is associated with an excess risk of mortality from cancers and cardiovascular disease²¹. Worldwide, osteoarthritis affects 60% of adults aged >65 years and is a major cause of disability; neither the prevalence nor impact of osteoarthritis have been assessed in HIV-positive adults.

Menopause

Around a third of those living with HIV in the UK are female. Whilst HIV appears to be associated with an earlier onset of the menopause²², the clinical implications of this for cognitive function, BMD and fracture risk, cardiovascular disease and lipid/glucose metabolism²² are unclear.

Antiretroviral drug use

Older individuals starting cART generally experience better virological responses but poorer immunological and clinical outcomes than their younger counterparts²³. Laboratory abnormalities and temporary discontinuations of cART due to toxicities are common^{23,24}. Detailed prospective studies on the pharmacokinetic characteristics of antiretroviral drugs are required to determine the optimal drug concentration and toxicity threshold in this population.

Older individuals experience changes in several elements of drug pharmacokinetics, including absorption, distribution, metabolism, and elimination. Furthermore, older HIV-positive people may be treated with several therapeutic agents that may interact with antiretroviral drugs²⁵. Data from other drugs suggest that elderly patients require lower doses to achieve therapeutic efficacy but may experience adverse events at lower concentrations. Plasma concentrations of some HIV protease inhibitors are higher in those aged >40 years²⁵.

Transmembrane drug transporter (i.e. p-glycoprotein) expression and function increases with older age, which may contribute to altered drug effects, drug toxicity and drug-drug interactions. Finally, reduced glomerular filtration rate that may occur in older people may lead to impaired elimination of drugs undergoing renal excretion, resulting in increased potential for toxicity.

3.3 Justification for the study

Currently, there is no large study on HIV and the effects of ageing in the UK and Ireland. Internationally, several research groups have developed initiatives in this area, but most of these studies are either limited by size, or are still at the recruitment stage. For example, the Hawaii Aging with HIV (HAWH) cohort has been running for several years but includes only around 60 HIV-positive individuals. Furthermore, studies are often hampered by the lack of appropriately selected and matched control groups, which limits the conclusions that can be reached regarding any associations with age and/or HIV status.

3.4 Study team

The study will bring together a team of leading HIV clinicians and academic researchers with extensive experience in the conduct and analysis of longitudinal studies in the HIV setting. Most members of the research team have ongoing projects in this field. For example, [name] has an established research programme on CNS toxicities in HIV-positive people. [name] has led a large international collaborative study on the effect of ageing on cART outcomes²⁶. [name] has conducted several studies of the effects of antiretrovirals on renal function, phosphate and vitamin D homeostasis, bone turnover and BMD. [name] runs a multidisciplinary clinic for those aged ≥ 50 years. [name] research focuses on the pathogenic mechanisms underlying long-term comorbidities of HIV infection. Over the past five years, the team has co-authored >300 peer-reviewed publications, and has attracted >£20 million in research funding. Studies conducted by the group have contributed to guidelines to recommend cART for all HIV-positive patients with CD4 counts <350 cells/mm³, and for the clinical monitoring of those living with HIV in the UK.

3.5 Summary

Our study, by enrolling both younger and older HIV-positive individuals with a matched HIV-negative control group, will be in the unique position to determine the effects of ageing and HIV status on chronic HIV-infection. In addition, results from this study will be well placed to assist in informing future HIV treatment guidelines on the monitoring of chronic HIV infection in older subjects and assisting in the design of future interventional studies for the treatment of age associated co-morbidities.

4.0 Study Plan

Aim:

1. To analyse the incidence and outcomes of co-morbidities in older-HIV-positive people and their relationship with demographic/clinical factors.
2. To evaluate associations between antiretroviral drug concentrations and age, and to assess the potential impact of age on drug efficacy, drug-drug interactions and co-morbidities.
3. To contribute to the development and implementation of evidence-based recommendations for the clinical monitoring of older HIV-positive patients.

Design:

Multicentre, prospective, observational study over 3 years

Our study will describe the impact of advancing age on the experience of living with HIV in England and Ireland. To address this we will establish cohorts of HIV-positive people aged >50 and <50 years as well as demographically matched HIV-negative people aged >50 years.

4.1 Study population

Inclusion Criteria

Older HIV-positive cohort (n=1000):

- documented HIV infection
- age ≥ 50 years at study entry
- self defined white or black African ethnicity
- likely route of HIV acquisition via sexual exposure
 - Either by male to male exposure if white or by heterosexual exposure if white or black African
- able to comprehend study patient information leaflet

Subjects with primary HIV infection are eligible and investigators are encouraged to recruit such subjects.

Our target population (those of white or black African ethnicity and those infected with HIV via sexual routes) has been chosen as these groups represent the vast majority of older HIV-positive individuals attending for care in the UK; analyses of other groups (e.g. injection drug users, those infected through blood/blood products and transgender individuals), who may have very different needs and outcomes, would likely be under-powered.

Younger HIV-positive cohort (n=500):

- documented HIV infection
- age < 50 at study entry*
- self defined white or black African ethnicity
- likely route of HIV acquisition via sexual exposure
 - Either by male to male exposure if white or by heterosexual exposure if white or black African.
- able to comprehend study patient information leaflet

* this group will comprise of at least 150 subjects in each of the following age groups: 20-29, 30-39, 40-49 years. Recruitment will be monitored by the Study Monitoring Team

HIV-negative cohort (n=500):

- documented negative HIV test at screening
- age ≥ 50 years at study entry
- self defined white or black African ethnicity
- registered with a General Practitioner and gives permission for contact with that GP.

Exclusion Criteria

- in the opinion of the investigator, those unable or unwilling to comply with the requirements of the study
- life expectancy less than 6 months

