4.3 Study Objectives

Clinical manifestations

- To describe the incidence and presenting features of serious medical conditions (such as cardiovascular, liver, renal disease, cancer and fragility fractures) in the three cohorts.
- To describe the outcomes of serious medical conditions (including time to recovery/resolution, where applicable, the incidence of complications and use of health-care).
- To compare NC function in the three cohorts, and to identify predictors of NC function.
- To compare the levels of musculoskeletal pain in the three cohorts, to identify predictors of this and to describe the health-care needs of those affected.
- Among women, to assess the effects of menopausal status on cardiovascular disease, BMD and lipid/glucose metabolism.

Antiretroviral pharmacokinetics and drug interactions

- To describe plasma (or, where appropriate, intracellular) concentrations of antiretroviral agents (tenofovir, non-nucleoside reverse transcriptase, protease, integrase and entry inhibitors) at baseline in the older HIV-positive cohort, and to compare these to those seen in younger HIV-positive patients.
- To describe the incidence of toxicities/drug discontinuations and immunological/virological responses to cART in the HIV-positive cohorts and to assess correlations between these events and plasma drug concentrations.
- To describe the level of poly-pharmacy in the older HIV-positive cohort and thus the potential for/prevalence of unwanted drug-drug interactions.
- To determine whether accumulation of renally-excreted antiretroviral drugs (e.g. tenofovir) increases their potential to cause renal injury in older HIV-positive people.

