5.3 Visit 2 (1st year follow up visit)

This follow up visit will be performed as per schedule of visits (2.0).

Only HIV-positive cohorts will be invited to undertake this visit with this visit expected to take 1 hour.

The following will be assessed:

- Changes to lifestyle and socio-economic status over the past year.
- Significant clinical events occurring over the past year: dates of onset and resolution, use of medical services, changes to antiretroviral and other medications, and resulting ongoing health concerns.
- Blood pressure will be estimated using an automated device.
- Details of access to health care services over the past year: visits to the general practitioner, hospital, counselors, psychiatrists, psychologists and medical investigations performed (information obtained by direct questioning and through HIV note review). Permission will be sought to contact the patient's general practitioner and/or hospital for further details.

- Most recent laboratory tests will be recorded: renal, liver, lipid and bone profiles, glucose, full blood count, sexual health screen, hepatitis C serology (Within the past year)
- Concomitant medications: start/stop dates; dose; dosing frequency; side effects.
- Fracture occurrence and fracture risk (see study questionnaire in appendix 1)
- Regional and widespread pain.

5.3a Visit 2 (1st year follow up visit) for HIV negative participants.

These participants will be contacted by telephone by arrangement with the study nurse. They may be asked to attend the clinic in order to facilitate this visit.

Details of any changes in circumstances or illnesses and medication will be documented.

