5.4 Visit 3 (2nd year follow up visit)

This follow up visit will be performed as per schedule of visits (2.0).

This visit is expected to take 1-2 hours; if possible the subject should attend fasted. The following information will be collected:

- Changes to lifestyle and socio-economic status over the past year.
- Significant clinical events occurring over the past year: dates of onset and resolution, use of medical services, treatments, and resulting ongoing health concerns.
- Details of access to health care services over the past year: visits to the general practitioner, hospital, counselors, psychiatrists, psychologists and medical investigations performed (information obtained by direct questioning and through HIV note review). Permission will be sought to contact the patient's general practitioner and/or hospital for further details.
- Measurement of hand grip strength using an automated device.
- Simple measurement of walking speed over a distance of 15 feet (457 cms).
- Blood pressure will be estimated using an automated device.
- Concomitant medications: start/stop dates; dose; dosing frequency; side effects.
- Fracture occurrence and fracture risk (see study questionnaire in appendix 1).
- DXA scan for bone mineral density (full body DXA where available) (within 30 days of clinic appointment)
- Neurocognitive function: specific memory and cognitive testing assessing cortical and sub-cortical function.
- Respiratory questionnaire
- Regional and widespread pain.
- Quality of life questionnaire.
- Most recent laboratory tests will be recorded (assessed in the HIV-negative cohort): renal, liver, lipid and bone profiles, glucose, full blood count, sexual health screen, hepatitis C serology (within the previous year)
- Blood (serum, plasma, and PBMC) and urine samples: stored for subsequent projects of the potential pathogenic mechanisms underlying age-related diseases. This will include assessment of vitamin-D and PTH
- Blood (plasma) will be collected for pharmacokinetic analysis (including but not limited to antiretroviral drug exposure)

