6.0 Study Specific Procedures

6.1 DEXA scanning

All study subjects will undergo a regional (hip and spine) and whole body DXA scan where available (only if urinary β hcg is negative in female subjects under the age of 50). Total and regional bone mineral density Z and T scores will be estimated and total and regional fat and lean mass calculated. All scans will be performed by medical staff and reported by a consultant radiologist and should be performed within 30 days of the clinic visit.

The reports of the scans will be sent to the patients GPs where permission for contact is in place. In the cases where no permission is granted for GP contact, the results will be sent to the health care professional in charge of that patient within the clinic. In all cases any abnormalities detected will therefore be actioned.

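### GP registration and permission for GP contact are entry conditions in the HIV-negative cohort only and are not recorded in the HIV-positive cohorts, so cross-cohort summaries of GP use are open to a difference that the data could not examine

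*Combined protocol and SAP*

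**What the plan says.** In section 4.1 the HIV-negative list ends with the condition that the participant is "registered with a General Practitioner and gives permission for contact with that GP". The lists for the older and younger HIV-positive cohorts contain no GP condition, and neither do the exclusion criteria shared by all three cohorts.

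For HIV-positive participants, GP contact is a matter for follow-up. Section 5.3 says "Permission will be sought to contact the patient's general practitioner and/or hospital for further details", and 5.4 repeats this for Visit 3. Section 6.1 plans for refusals: "In the cases where no permission is granted for GP contact, the results will be sent to the health care professional" in charge at the clinic.

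GP use is collected. At Visit 3 (5.4) the record of health-care access covers "visits to the general practitioner, hospital, counselors, psychiatrists, psychologists and medical investigations performed", and this applies to all cohorts. Question 76 of the Appendix 1 questionnaire asks people with recent aches or pains whether they have consulted their family doctor about them. Health-care use is part of an objective in 4.3: "To describe the outcomes of serious medical conditions (including time to recovery/resolution, where applicable, the incidence of complications and use of health-care".

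The Visit 1 list in 5.2 covers socio-economic status in some detail, including immigration status, income and housing. It has no item for GP registration or for permission to contact a GP. Section 8.1 mentions no restriction or adjustment for either.

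**The concern.** An entry rule tied to engagement with primary care, applied on one side of a comparison, can create a difference in primary-care use that has nothing to do with HIV. A person without a GP can be in an HIV-positive cohort and will have few or no GP visits to report. The same person cannot be in the HIV-negative cohort. The GP as a source of further detail on clinical events is likewise secured at entry for every HIV-negative participant, but is optional for HIV-positive participants.

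This matters because the study's stated advantage (3.3 and 3.5) is a properly selected and matched control group. It matters more because neither item is recorded. If the difference is negligible, the investigators cannot show it. If it is not, they cannot restrict or adjust for it.

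**Working it through.** **1. The entry rules side by side (section 4.1)**

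- HIV-negative (n=500): GP registration and permission for contact both required.
- Older HIV-positive (n=1000) and younger HIV-positive (n=500): neither required.

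The rule therefore bears on HIV-positive v HIV-negative contrasts. It creates no imbalance between the two HIV-positive cohorts. Since every HIV-negative entrant has given permission, the participants without permission foreseen in 6.1 can, at entry, only be HIV-positive. Section 6.1 gives no share, and it concerns permission, not registration.

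**2. The two halves of the rule act differently**

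- Not registered: few or no GP visits occur, so reported GP use falls.
- Registered but permission refused: GP visits can still be reported, because 5.4 obtains them by direct questioning. Only confirmation from the GP is lost.

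**3. The plan's own figures**

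The plan gives no size or power figure for health-care use. The nearest benchmark is in 8.1: more than 95% power at the 5% level for a 10-point difference between the older HIV-positive cohort and another cohort, around 40% (neurocognitive impairment) or 63% (pain). The check used two proportions and a two-sided 5% level (sidedness is not stated):

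power = Φ{ [ |p1 − p2| − 1.96 √( p̄(1−p̄)(1/n1 + 1/n2) ) ] / √( p1(1−p1)/n1 + p2(1−p2)/n2 ) }

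- 1000 v 500: 95.7% (40% v 50%), 97.0% (40% v 30%), 96.0% (63% v 53%), 97.5% (63% v 73%). The stated figure is reproduced.
- 900 v 450: 93.7% to 96.1%. This was run because 540/0.40 = 1350 and 850/0.63 ≈ 1349, which is 90% of 1500.

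Ten points is thus the scale of difference that the plan treats as worth detecting.

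**4. Illustration of the possible size (assumed inputs)**

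Let p be the proportion of registered people with any GP visit in a year, equal in both cohorts (no HIV effect). Let u be the share of HIV-positive participants who are not registered and so report none. The documents give neither value.

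- Expected HIV-negative proportion: p
- Expected HIV-positive proportion: p(1 − u)
- Spurious difference: p − p(1 − u) = p × u

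| p | u = 0 | u = 2% | u = 5% | u = 10% | u = 20% |
|---|---|---|---|---|---|
| 0.60 | 0 | 1.2 | 3.0 | 6.0 | 12.0 |
| 0.75 | 0 | 1.5 | 3.75 | 7.5 | 15.0 |
| 0.90 | 0 | 1.8 | 4.5 | 9.0 | 18.0 |

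Entries are percentage points. At p = 0.75 and u = 5%, HIV-positive participants would show 0.75 × 0.95 = 71.25% against 75%, a difference of 3.75 points.

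**5. Other cohort differences, which act in other ways**

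- HIV-positive participants are sampled from lists of clinic patients (4.2.1), so they are in specialist care by design. HIV-negative participants come from clinics, press, community organisations, internet sites and churches (4.2.2).
- HIV note review (5.3, 5.4) and linkage to existing HIV cohort data (4.2) exist only for HIV-positive participants.
- At one year, health-care access is listed for the HIV-positive visit (5.3) but not for the HIV-negative telephone contact (5.3a), which covers circumstances, illnesses and medication.

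These tend towards fuller recording in HIV-positive people. The GP rule tends towards fuller GP use and GP confirmation in HIV-negative people. The documents do not show which prevails.

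**6. Cost in precision of a restricted comparison**

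At p = 0.75, the 95% half-width for a difference is 1.96 √(0.1875 × (1/1000 + 1/500)) = 4.6 points. If 20% of the older HIV-positive cohort did not meet the condition, it becomes 1.96 √(0.1875 × (1/800 + 1/500)) = 4.8 points. Both ignore loss to follow-up.

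**The case against.** The strongest reply is that the plan contains no test this would distort. The health-care objective in 4.3 is descriptive and concerns people who already have a serious condition. Section 8.1 confines statistical comparisons to the prevalence and incidence of clinical events, and none of these is defined as GP-diagnosed. Laboratory results, DXA, neurocognitive testing and the pain assessment do not depend on a GP. Direct questioning captures GP visits whether or not permission is given. This stands. It limits the point to descriptive summaries read across cohorts and to events for which GP contact supplies confirmation. It does not remove the point, because 4.3 describes serious conditions in all three cohorts and 5.4 collects GP visits in all of them.

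A second reply is that almost everyone may be registered. That may be so, and the difference would then be close to zero. The documents give no share, and as planned the data would not supply one.

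It can also be said that permission status must already be known at site level, because 6.1 routes scan reports by it. That is fair, but the Visit 1 list does not make it a data item. It does make the item easy to collect.

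**Conclusion.** The asymmetry is real and is not handled in the plan. Cross-cohort summaries of GP use, and comparisons of conditions confirmed through GP contact, are open to a selection and ascertainment difference of unknown size and unknown net direction. On the assumed ranges (p 0.60 to 0.90, u 0 to 20%) the registration half alone gives 0 to 18 points, and about 4 points at 75% GP use and 5% unregistered. These figures rest wholly on assumptions about registration and GP use.

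A reader might infer more, and the documents do not support it:

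- That HIV-positive people will appear to have less disease. Clinic-list sampling, HIV note review and cohort linkage may push the other way.
- That a calculable false-positive rate follows. It would belong to a test of GP use that 8.1 does not contain, at a non-registration share that nobody has reported.
- That 6.1 shows some participants to be unregistered. It shows only that permission may be refused.
- That the criterion "able to comprehend study patient information leaflet", listed for the HIV-positive cohorts only, biases the neurocognitive comparison. Written consent before screening (5.1) and the shared exclusion of people unable to comply apply to all three cohorts, so similar people are unlikely to enter the HIV-negative cohort.
- That the synopsis contradicts 4.1 by omitting the GP rule. Its list is labelled a summary.

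**What to change.** Keep the HIV-negative entry rule. In 5.2 and the eCRF, add two yes/no items at Visit 1 for the HIV-positive cohorts: registered with a GP, and permission for GP contact given.

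In 8.1, state that HIV-positive v HIV-negative summaries of GP use and of GP-confirmed diagnoses will be shown for all participants and repeated, as a sensitivity analysis, among those who are registered and have given permission. The restriction needs both parts, because the entry rule has both. It should support the all-participant summary and not replace it: if HIV status itself affects registration or willingness to give permission, restricting could remove part of a real difference.

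The cost is two eCRF fields, one extra analysis and a smaller HIV-positive sample in that analysis. Even a 20% loss from the older cohort widens the 95% half-width only from 4.6 to 4.8 points in the example above. The restriction puts the cohorts on the same GP condition. It does not remove the differences in recruitment source or note review, which should be stated beside the results.
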